TMH	Tear meniscus height
US	United States
WOCBP	Women of childbearing potential
WT	Wear time

1 INTRODUCTION

The worldwide contact lens (CL) market in 2016 was estimated to be \$7.2 billion dollars in value.¹ Yet drop out from CL wear continues to be one of the major reasons for slow overall growth of this market with the most commonly cited reasons for drop out as 'discomfort and dryness'.^{2,3}

In 2013, the Tear Film and Ocular Surface Society (TFOS) defined CL dryness (CLD) as: 'a condition characterized by episodic or persistent adverse ocular sensations related to CL wear, either with or without visual disturbance, resulting from reduced compatibility between the contact lens and the ocular environment, which can lead to decreased wearing time and discontinuation of lens wear'.⁴

Given the progression of CLD from 'struggling with symptoms of discomfort', to 'reduced wear time' and finally 'discontinuation of CL wear', it is important for practitioners to have access to appropriate management strategies. CLD is multifactorial and some strategies involve CL-related modifiable factors such as material or wear modality.⁴ Other areas of management address patient-related factors such as low tear volume or poor tear quality. Some studies have demonstrated reduction in dryness symptoms and increase in CL wear times via either intracanalicular⁵ or inferior punctal occlusion.⁶ These methods essentially increase the volume of tears in the eye. An alternative approach to increasing tear volume would be to stimulate tear production. The TrueTear device has been shown to do this.^{7,8}

Rationale for TrueTear (Intranasal Neurostimulator Device)

The nasolacrimal reflex is a well-established pathway by which nasal stimuli promote both resting basal and bolus tear secretion.^{9,10} The reflex plays a functional role in expelling foreign bodies or irritants from the nose by secreting tears into the nasal cavity via the nasolacrimal duct upon stimulation by the irritant.^{11,12}

Reflex activation of the lacrimal glands is also one of the body's primary compensatory mechanisms for addressing ocular surface dryness.¹³⁻¹⁷ Unfortunately, over time, an arid environment and resulting inflammation results in damage to the afferent nerves innervating the cornea, compromising the reflex response, and ultimately leading to an even drier ocular surface.

Studies have demonstrated that intranasal stimulation via TrueTear application results in a statistically significant increase in tear production measured by the Schirmer test^{7,8} and as such may provide a novel option for relief of CLD. This study is focused on quantifying the change in both comfortable wear time and total wear time following use of TrueTear for 30 days compared to a group using TrueTear sham control.

2 OBJECTIVES

The objective of this study is to evaluate the increase in comfort and comfortable CL wear time associated with application of TrueTear (active intranasal neurostimulation) compared with application of TrueTear sham control (intranasal application which is not electrically active) in symptomatic CL wearers.

The primary outcome variables for this study are:

- Contact Lens Dry Eye Questionnaire (CLDEQ-8)
- comfort ratings
- comfortable wear time (CWT)
- total wear time (total WT)

3 HYPOTHESIS

Improvements in CWT and comfort ratings in participants using TrueTear (active device) will be superior to those participants using the TrueTear sham control.

4 MATERIALS AND METHODS

[figure not shown]
[figure not shown]
4.1 STUDY DESIGN

4.1.1 OVERALL DESIGN

This is a prospective, double-masked, controlled, randomized by device (TrueTear vs TrueTear sham control), parallel arm study, with up to 6 study visits including a screening visit. Study participants (n=80) will be habitual, symptomatic wearers of daily disposable (DD) or reusable hydrogel and silicone hydrogel (SiHy) CLs. Symptomatic participants will be recruited, with a minimum average wear of 2 days/week and ≥ 3 hours of wear/day. It is expected that the majority of symptomatic wearers will be wearing the lenses on average 4-7 days/week. Wearers will be randomized to use the active device or the intranasal sham control.

Visit schedule:

There will be up to 6 study visits and cumulative total time commitment for the study is approximately 6 hours. [REDACTED] Permitted time interval between V1 and V2 is 7- 45 days.

4.1.2 TRUETEAR DESCRIPTION

The TrueTear device delivers small electrical currents to the inner cavity of the nose, activating nerves that stimulate the body's natural tear production. The device is approved in Canada to increase tear production during stimulation. Use of the product to relieve CLD is investigational.

The device consists of four distinct parts (Figure 3):

1. A reusable Base Unit which produces the electrical stimulation waveform.

2. A disposable Tip that inserts into the nasal cavity and stimulates the target intranasal tissue.
3. A reusable Cover to protect the Tip.
4. A Charger which recharges the battery inside the Base Unit

TrueTear Base Unit with and without Cover

TrueTear Base Unit with Disposable Tips
(Front and Back)

TrueTear System

Figure 3: TrueTear System Components

4.1.2.1 BASE UNIT

When activated, the Base Unit provides electrical pulses to the Tip. The strength of these pulses is controlled by two buttons, with five different intensity levels available, indicated by the number

of illuminated LEDs on the Base Unit. The device internally records the time and duration of device use.

4.1.2.2 DISPOSABLE TIP

The disposable Tip is specially designed to allow the participant to easily apply stimulation to the target areas within the nose. The Tip attaches to the Base Unit and contains hydrogel (similar to the material used in contact lenses) that contacts the inside of the nose to provide stimulation. Each tip may be used up to 24 hours. After 24 hours, the used tip should be discarded and a fresh tip should be attached. A separate Cover can be used to protect the Tip and Base Unit when the device is not in use.

4.1.2.3 COVER

The Cover may be placed over the top of the Tip attached to the Base Unit for protection in between uses.

4.1.2.4 CHARGER

The Base Unit may be recharged by removing the Tip and placing the Base Unit onto the Charger. Charging typically takes under 4 hours, and a green LED indicates that the process has completed.

4.1.3 TRUETEAR SHAM CONTROL

The comparator arm in this study is the TrueTear sham device, which is not electrically active, and will be applied intranasally. The sham device (Figure 4) consists of a Base Unit and Tip Assembly that have been modified so that the depth to which the probes are inserted into the nose is limited. All other parts of the device are identical. This sham device is also electrically nonfunctional; the device powers on, but no electrical stimulation energy is delivered through the Tip Assembly. Participants are to be instructed to place only the tips of the device into both nostrils simultaneously so that the nose stop on the device touches the participant's septum.

[figure not shown]

Figure 4: TrueTear Sham Control Base Unit with Disposable Tips

4.1.4 RANDOMIZATION

A randomization schedule will be generated using a web-based program: (www.randomization.com) with stratification by groups based on frequency of lens wear during the week. The final study randomization schedule will be generated [REDACTED] [REDACTED] and provided to the research assistants for the study. Study investigators will remain masked to the randomization schedule until the study is completed and the database is locked.

4.1.5 MASKING

The study will be double-masked with both participant and site personnel interacting with the participant being masked. The participants will be aware that they will be randomized to an intranasal device with only one being electrically active. Neither participant or site personnel interacting with the participant will be told which device the participant is randomized too.

Researchers tasked with collecting study data will be masked throughout the study. The initial use of TrueTear or TrueTear sham control in V2-1 and reviewing the procedure for proper use of the device in V2-1, V2-2 and V3 will be conducted by either research assistants, unmasked investigators or study sponsor representatives.

4.2 STUDY POPULATION

4.2.1 SAMPLE SIZE CALCULATION

Due to the exploratory nature of this study, the planned sample size was determined empirically.

4.2.2 NUMBER OF PARTICIPANTS

Up to 120 eligible participants will be dispensed / randomized with study products, with a target of 80 completing the study. Informed consent will be obtained for all participants prior to their enrolment in the study.

4.2.3 INCLUSION AND EXCLUSION CRITERIA

A person is eligible for inclusion in the study if he/she:

4. In at least one eye, has a cotton swab nasal stimulation Schirmer test score at least 4 mm greater than 3 minute Schirmer with anesthesia basal score in the same eye at the Screening Visit
5. Is an adapted soft contact lens wearer and currently wears lenses an average of at least 2 days per week, with an average minimum wearing time of 3 hours each day over the past month, AND is able and willing to wear lenses for at least 6 hours on four study day visits.

■ [REDACTED]

■ [REDACTED]

7. Has at least 20/40 visual acuity in both eyes with CL correction
8. Is symptomatic using Young's categorization as outlined in this protocol.

A person will be excluded from the study if he/she:

4.2.4 REPEATED SCREENINGS

In some circumstances a repeated screening may need to be scheduled. Examples include, but are not limited to:

1. Incomplete information available at time of screening to determine eligibility (e.g. current lens brands worn, history from current eye care practitioner, etc.)
2. Study procedures unable to be completed in time scheduled for visit;
3. Study products not available at the time of the screening visit;
4. A transient health condition which may affect the eye(s) (e.g. a common cold, active allergies, fatigue, etc.)
5. Seven days after the final use of short term medications (e.g. antibiotics, antihistamines, etc.)
6. Reassessment of baseline ocular conditions (e.g. corneal and/or conjunctival staining, scars, etc.)

The maximum total number of repeated screenings permitted will be 1.

4.3 STUDY MATERIALS

4.3.1 LENSES

The participant will continue with their habitual CLs throughout the study. A one month supply of their current lenses will be dispensed to the participant at V2-1.

The participant must bring an unopened package of their current CLs to the screening visit. The specification of the CLs will be noted, and a one month supply of the lenses ordered by the CCLR. The CLs must be commercially available in Canada.

4.3.2 LENS CARE SYSTEM

A lens care system will be used when a participant habitually wears anything other than soft daily disposable CLs. They will continue with their habitual lens care system throughout the study. A one month supply of their lens care system will be dispensed to the participant at V2-1.

The participant must bring their lens care system with them to the screening visit. The type of system will be noted, and a one month supply ordered by the CCLR. The lens care system must be commercially available in Canada.

4.3.3 DEVICE (TRUETEAR AND TRUETEAR SHAM CONTROL)

Either a TrueTear or TrueTear sham control device will be dispensed at V2-1 along with a supply of tips. A second supply of tips will be dispensed at V4. Additional tips may be dispensed as required to allow participant access to a new tip every 24 hours as per usage guidelines. This may be required if the participant is seen at the end of each visit window for example.

4.3.4 ARTIFICIAL TEARS AND REWETTING DROPS

The use of artificial tears / rewetting drops is not permitted throughout the study. A participant must cease use of artificial tears / rewetting drops at least three days prior to visit 2, and must commit to not using any of these products throughout the duration of the study period.

4.3.5 ORDERING CONSUMABLES

The sponsor will provide TrueTear and TrueTear sham control devices (base units and associated tips). The CCLR will order CLs and CL care systems for each participant.

4.3.6 CONTACT LENS / LENS CARE PRODUCT ACCOUNTABILITY

Accountability logs will be kept to include the number of lenses and lens care system bottles received, dispensed, unused and returned to sponsor (where relevant). All products dispensed to participants will be recorded in the study binder.

4.3.6.1 TRUETEAR AND TRUETEAR SHAM CONTROL ACCOUNTABILITY

Each Base Unit of TrueTear and TrueTear sham control devices have a unique serial number and the serial number of the Base Unit used by each participant will be recorded on the appropriate case report form and device accountability log. The removable disposable Tip (for either TrueTear

[figure not shown]
or TrueTear sham control), is provided in an air tight sealed pouch, which is labelled with the lot number and expiration date. The lot number of the Tips provided to a participant will also be recorded on the appropriate case report forms and on the device accountability log. Tips should not be used beyond the expiration date provided on the pouch.

4.4 SCHEDULED AND UNSCHEDULED VISITS

This study has a total of 6 study visits, including the screening visit.

4.4.1 SCREENING

The investigator will determine participant eligibility using the inclusion and exclusion criteria.

4.4.3 UNSCHEDULED VISITS

An unscheduled visit is defined as an interim visit requested by the participant or investigator due to an unanticipated problem. Data recorded at these visits will be entered into the database. Only relevant and applicable unscheduled visit information will be included in the final report as deemed necessary by the lead investigator.

4.5 STUDY PROCEDURES

[REDACTED]

[REDACTED]

[REDACTED]

[REDACTED]

[REDACTED]

[REDACTED]

[REDACTED]

STANDARD OPTOMETRIC PROCEDURES:

4.5.1 CASE HISTORY

Demographic information from the participant will be obtained, including age, gender, CL details, artificial tear use, and relevant health and medical information.

4.5.2 DETERMINATION OF SYMPTOMS

Patients will be considered symptomatic based on Young's categorization.⁴ This corresponds to the dark grey areas in Table 3 below:

Table 3: Young's categorization for contact lens dry eye score

Categorization grid for the Contact Lens Dry Eye score.

		Frequency of dryness				
		Never	Rarely	Sometimes	Frequently	Constantly
Intensity of late-day dryness	Never have it – 0	No	No	No	No	No
	Not at all intense – 1	No	No	No	No	No
	2	No	No	Marginal	Marginal	Marginal
	3	No	No	Yes	Yes	Yes
	4	No	No	Yes	Yes	Yes
	Very intense – 5	No	No	Yes	Yes	Yes

Note: Score derives from the combination of responses to frequency and intensity of dryness late in the day. Dark grey, Dry; light grey, Marginal; white, Not Dry.

4.5.3 VISUAL ACUITY

Visual acuity will be measured using high contrast computer-generated acuity charts. Participants will be asked to read letters that progressively decrease in size on a computer screen located at a distance of 6 meters.

4.5.4 BASELINE OCULAR MEASURES

4.5.4.1 PRE-LENS NON-INVASIVE TEAR BREAK UP TIME

Pre-lens non-invasive tear breakup time (NITBUT) will be assessed using a placido-disc device. The rings of the disc will be projected onto the tear film and the time to first disruption of that image in between blinks will be noted. An average result will be calculated from three measures in each eye.

4.5.4.2 TEAR MENISCUS HEIGHT (TMH)

An image of the tear meniscus in both eyes will be taken using the Oculus Keratograph 5M instrument. TMH will be calculated as an average of two measures taken using the on-screen calipers.

4.5.5 CONTACT LENS ASSESSMENT

Contact lens wettability and deposition will be graded using a 0-4 scale (0.25 steps), 0 = excellent, 4 = poor

4.5.6 THREE-MINUTE BASAL SCHIRMER TEST WITH TOPICAL ANESTHESIA

At the Screening Visit, one basal Schirmer test with anesthesia will be performed followed by a Schirmer test with cotton swab nasal stimulation. The Schirmer test with topical anesthetic will be used to assess tear production using the following steps:

1. One drop of topical anesthetic drops such as 0.5% proparacaine hydrochloride or equivalent should be instilled in each eye of the participant.
2. The participant will be instructed to keep the eyes gently closed for one minute.
3. After opening the eyes and allowing the eyes to recover for approximately one additional minute, excess moisture in the inferior fornix is gently removed with a spear.
4. Schirmer strips (35 mm x 5 mm size filter paper strip) will be placed in each eye at the junction of the middle and lateral thirds of the lower eye lid.

5. Under ambient light, the participant will be instructed to look forward and to blink normally during the course of the test. The test should be performed in a room with no direct air on the participant's face.
6. The Schirmer strips should remain in place until three minutes have elapsed or both strips have reached maximum score.
7. After three minutes, strips will be removed from both eyes and the amount of wetting will be recorded. The strips should be taped to the CRF.
8. Following this test, a three-minute Schirmer test with cotton swab nasal stimulation will be performed (see Section 4.6.2).

4.5.7 DETERMINATION OF REFRACTION

Participants will have a measure of their ocular prescription taken using an autorefractor. A full subjective refraction will only be conducted where it is not possible to correct either eye to better than 0.20 logMAR with their habitual contact lenses.

4.5.8 BIOMICROSCOPY / OCULAR HEALTH EVALUATION

The participant will sit behind a slit lamp and the following will be assessed.

4.5.8.1 BULBAR AND LIMBAL HYPEREMIA

The redness of the bulbar and limbal conjunctiva of both eyes will be assessed using the EFRON Grading scale (0 to 4, 0 = no redness).

4.5.8.2 CORNEAL AND CONJUNCTIVAL STAINING

A sodium fluorescein strip, wetted with a few drops of saline, will be applied to the superior bulbar conjunctiva of both eyes. Staining will be graded using the CCLR scale (0 to 100, 0 = no staining) while viewing with cobalt blue light through a Wratten no. 12 barrier filter.

4.5.8.3 PALPEBRAL CONJUNCTIVAL HYPEREMIA AND ROUGHNESS

The redness and roughness of the upper and lower eyelids (tarsal plate zone 2) will be assessed using the CCLR scale (0 to 100, 0 = no redness/roughness).

4.5.9 COMFORT RATINGS

Participants will be asked to complete subjective ratings at the study visits and at home on certain study days. They will record their responses on an online database [REDACTED]

[REDACTED] Responses will be captured at screening, on study day 0 (at V2-1, V2-2), and subsequently at days 3, 6, 8, 12, 15, 18, 21, and 24 where comfort will be recorded after lens insertion, after 2 hours of lens wear and prior to lens removal at the end of the wearing day. Comfort will be assessed on a 100 point scale with a score of 0 indicating "Extremely uncomfortable" and a score of 100 indicating "Extremely comfortable." Verbal instructions on how to complete the diary will be provided and email reminders will be sent to the participant for each rating. The CLDEQ-8 questionnaires will also be completed at Visit 1, 4 and 5 using the [REDACTED] on the participant's phone. The individual assessments on the CLDEQ-8 questionnaire will be summarized to provide a score of 1 to 37.

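### The planned CLDEQ-8 comparison (12.1, Table 4) is unbiased but uses unadjusted change from a screening score taken 7 to 45 days before dispensing; adjusting for that score would gain precision with no new data

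*Combined protocol and SAP*

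**What the plan says.** Section 2 lists CLDEQ-8 among the primary outcome variables. Section 4.5.9 gives its schedule: "The CLDEQ-8 questionnaires will also be completed at Visit 1, 4 and 5". Section 12.1 identifies V1 as the Screening Visit.

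On timing, 4.1.1 says "Permitted time interval between V1 and V2 is 7- 45 days", and 4.3.3 says "Either a TrueTear or TrueTear sham control device will be dispensed at V2-1". Section 4.1.5 also places first use there ("The initial use of TrueTear or TrueTear sham control in V2-1"). The 100-point comfort rating, described in the same paragraph as CLDEQ-8, is already recorded at V2-1.

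On conditions between the two visits, 4.3.4 says "The use of artificial tears / rewetting drops is not permitted throughout the study" and also "A participant must cease use of artificial tears / rewetting drops at least three days prior to visit 2". The second sentence leaves open that drops are still used when the V1 score is given; the two sentences need to be reconciled.

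On analysis, Table 4 in 12.1 compares change from baseline between the arms at each visit. A Shapiro-Wilk test decides between a t-test and a Wilcoxon rank-sum test. No covariate model is listed. No SD, correlation or effect size is given, and the sample size was set empirically (4.2.1).

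**The concern.** A change score subtracts the whole baseline value. If that value was taken weeks earlier, possibly under different drop use, it follows the later score less closely, and the subtraction carries its noise into the comparison. A model that estimates the baseline slope removes only the part of the baseline that predicts follow-up.

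At stake is the width of the interval for the CLDEQ-8 difference. That matters here because the trial has no power calculation and, according to 12.1, its results may inform the power of later studies.

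**Working it through.** The plan states no figure to reproduce. All the variance inputs below are assumptions.

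**Inputs**
- From the documents: about 80 randomized; CLDEQ-8 at Visits 1, 4 and 5; a gap of 7 to 45 days; unadjusted change compared.
- Assumed: 40 per arm; two-sided 5% level; SD 6 at each time (variance 36) on a score that 4.5.9 describes as running from 1 to 37; correlation r of V1 with follow-up 0.6 or 0.7; a fraction f = 0 or 0.5 of participants using drops at V1; a shift D of 0 or 4 points on stopping them. Drop use adds f(1−f)D² = 0.5 × 0.5 × 16 = 4 to the V1 variance.

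**Step 1: bias.** V1 precedes device use in both arms. Elapsed time, stopping drops and regression to the mean (eligibility requires that a person "Is symptomatic using Young's categorization as outlined in this protocol") therefore have the same expectation in each arm. In four scenarios of 20,000 simulated null trials, the mean arm difference was at most 0.015 points and the type I error was 4.8% to 5.1%. In a separate 10,000-trial simulation with selection on V1 and a shared shift after it, the estimate was 0.003 SD for a true 0 and −0.497 SD for a true −0.5.

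**Step 2: planned change score against V1-adjusted model.**
Variance of change = Var(V1) + 36 − 2Cov, with Cov = 36r.
Adjusted variance = 36 − Cov²/Var(V1).

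| r, drops | Change score | V1-adjusted | Reduction |
|---|---|---|---|
| 0.7, none | 36 + 36 − 50.4 = 21.6 | 36 − 25.2²/36 = 18.36 | 15% |
| 0.6, none | 36 + 36 − 43.2 = 28.8 | 36 − 21.6²/36 = 23.04 | 20% |
| 0.7, f = 0.5, D = 4 | 40 + 36 − 50.4 = 25.6 | 36 − 25.2²/40 = 20.12 | 21% |
| 0.6, f = 0.5, D = 4 | 40 + 36 − 43.2 = 32.8 | 36 − 21.6²/40 = 24.34 | 26% |

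In interval width: √(18.36/21.6) = 0.92 and √(24.34/32.8) = 0.86, so 8% to 14% narrower. The 95% half-width, t × √(2 × variance/40), goes from 2.07 to 1.91 points in the first row and from 2.55 to 2.20 in the last. Estimating the slope costs about 1/(80 − 4) = 1.3% in variance, which is not deducted here.

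**Step 3: how far this depends on the inputs.** The difference between the two variances is (1 − b)² × Var(V1), with b = Cov/Var(V1). It is never negative, but it shrinks if eligibility narrows the spread of V1. In the simulation with selection directly on the V1 score (correlation 0.5 before selection), the standard error fell only from 0.2025 to 0.1957 SD, which is 3.4%. That is a harsh case, because eligibility uses a dryness grid and not CLDEQ-8 itself.

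**Step 4: adding a V2-1 score.** Residual variance, V1 alone against V1 and V2-1 together:
- Both correlate 0.6 with follow-up and 0.9 with each other: 23.04 to 22.36, a 3% reduction.
- Both 0.7, and 0.7 with each other: 18.36 to 15.25, a 17% reduction.
- V1 0.6, V2-1 0.7, 0.7 with each other, f = 0.5, D = 4: 24.34 to 17.66, a 27% reduction, or √(17.66/24.34) = 0.85 in width.
- V1 the better predictor (0.7 against 0.6): 0% to 8% reduction. In one simulated case (0.9 with each other) the estimator variance rose by 0.7%.

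Moving the unadjusted change score to V2-1 is not a substitute. The variance ratio, V1 change to V2-1 change, runs from 21.6/28.8 = 0.75 to 32.8/21.6 = 1.52, so it can lose precision.

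**The case against.** The strongest reply is that nothing here is an error. The study is exploratory, the hypothesis in section 3 names comfortable wear time and comfort ratings but not CLDEQ-8, and 12.1 allows additional analyses, so a V1-adjusted model could be added later. That stands, and it is why this is a suggestion. It does not remove the advantage of naming the model before the data are seen.

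A second reply is that the dependable gain comes from adjustment and not from a new questionnaire. That also stands. The 27% figure needs V2-1 to be the better predictor, a low correlation between the two baselines, half the participants on drops and a 4-point shift. The documents support none of these. A V2-1 covariate also has a cost: 12.1 excludes missing data points, so anyone without that score would leave the model, and about 3% missing would cancel a 3% gain.

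Three stronger readings are tempting. A reader might infer that the early baseline biases the arm comparison; randomization rules that out. A reader might infer that the plan misreads change within an arm as a device effect, but Table 4 lists no test of within-arm change. A reader might fault the plan for leaving baseline undefined, but 12.1 opens with redacted text, so its absence from the visible pages proves nothing.

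**Conclusion.** The point holds as a gain in precision that the plan leaves unused. The CLDEQ-8 arm comparison is not biased by the timing of its baseline. Adjusting for the V1 score already collected would lower the variance by about 15% to 26%, assuming correlations of 0.6 to 0.7 and equal SDs before any drop effect. Without a drop effect the range is 15% to 20%. The gain would be smaller if eligibility strongly narrows the V1 scores.

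The documents do not support reading the absence of a V2-1 questionnaire as a defect that must be repaired, because its added value may be close to nil. Section 4.4.2, Tables 1 and 2 and parts of 4.1.1, 4.5 and 12.1 are not visible and could hold a Day 0 questionnaire or a baseline definition. A hidden V2-1 questionnaire would, however, sit awkwardly with the explicit visit list in 4.5.9.

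**What to change.** In 12.1, compare the arms on CLDEQ-8 at Visits 4 and 5 with a linear model (ANCOVA) adjusting for the V1 score. Keep the rank-sum test on change as a sensitivity analysis. For this outcome the model replaces the choice of test by Shapiro-Wilk, and the stratified row of Table 4 needs the same edit. The cost is a few sentences and one degree of freedom. No participant is lost, because the change score already requires the V1 value.

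Optionally, in 4.5.9, add CLDEQ-8 at V2-1 before the first device application and enter it as a second covariate. State that participants without it stay in the analysis, for example by simple baseline imputation. State the recall period too, since one longer than three days could carry earlier drop use into the V2-1 score. The cost is one more eight-item questionnaire at an existing visit.
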